6.8.4. Missing Start Date, Stop Date, Severity, or Relationship for Adverse Event

The same conventions to address incomplete dates for prior and concomitant medications will also be used for AEs. Should an event have a missing severity or relationship, it will be classified as having the highest severity and/or strongest relationship to study treatment.

6.8.5. Missing Time of First Dose or Time of Last Dose

In case of missing time for first dose, it will be assumed that baseline measures that were to be taken prior to first dose according to the protocol were in fact taken prior to dosing.

In case the time of the last dose is not reported, time of dose will be assigned as the median dosing time from all prior doses for the subject, as subjects are to dose once per day at approximately the same time each day.

6.8.6. Incomplete Date and Time for a Subject-Reported Event

For HAE events reported with missing start date and/or time, stop date and/or time, or date and/or time reported that the worst symptoms of the event were over (“worst over”), the following algorithm will be applied:

- Missing start time but start date present:
The start time will be set to 12:00PM.
- Missing start date and time:
The start date will be set to the date for which the question was answered “Yes”. The start time will be set to 12:00PM
- Missing worst over time, but worst over date present:
The worst over time will be set to 11:59PM.
- Missing worst over date and time:
The worst over date will be set to the start date, the worst over time will be set to 11:59PM
- Missing stop time, but stop date present:
The stop time will be set to 11:59PM
- Missing stop date and time:
The stop date will be set to the worst over date, or if missing, the event start date, the stop time will be set to 11:59PM

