6.7.5. Derived Efficacy Endpoints

6.7.5.1. Event Rate

General Formula for Event Rate

In general, the formula for computing an event rate is the number of events meeting the event criteria divided by the duration of treatment during the reporting period of interest. Duration of treatment during the reporting period of interest = the last day in the reporting period – first day in the reporting period + 1.

$$\begin{aligned} \text{Event Rate} \left(\frac{\text{events}}{\text{month}} \right) \text{ During Reporting Period of Interest} \\ = \frac{\text{Number of Events} * 28}{\text{Duration of Treatment During Reporting Period in Days}} \end{aligned}$$

If the subject discontinues treatment early, any events that occur within 24 hours after last dose will be counted in the calculation of event rate and the additional 24-hour period will be included in the duration of the reporting period.

Subject-Reported Event Rate

Diary entries for events and investigator-collected events that are not captured in the diary are considered subject-reported events. The expert reviews each event and either confirms it as an event or rejects it as an event. For Part 3, there is no expert review of attacks, but an adjusted subject-reported attack rate will be computed based on a list of programmable requirements.

Subject-reported event rates will be computed for the entire dosing period only (ie, not for the effective dosing period or by month) for Parts 1, 2, and 3.

Adjusted Subject-Reported Attack Rate for Part 3

Because there is no expert-confirmation of attacks during Part 3, an adjusted subject-reported attack rate will be computed.

Subject-reported attacks must meet the following criteria (applied in order) for inclusion in the adjusted subject-reported rate computation:

- Attack must include at least 1 symptom of swelling
- Subject response to diary question, “In retrospect, could there be an alternative explanation for your symptoms other than an HAE attack (ie, allergic reaction, viral cold, etc)?” must be “no”

- Attack must be unique (attack begins > 24 hours from end of the prior attack), otherwise the event will be combined with and treated as a continuation of the preceding attack
- If untreated, attack must have a duration > 24 hours

Adjusted subject-reported attack rates will be computed for the following reporting periods and expressed in units of attacks/month where 1 month = 28 days:

- Part 3, by month
- Part 3, entire dosing period

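### In Part 3, an untreated stand-alone attack with no stop date, and no worst-over date later than its start date, always fails the 24-hour duration test because of the imputation and drops out of the adjusted rate

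*SAP*

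**What the plan says.** SAP 6.8.6 covers subject-reported events in general and makes no exception for Part 3: "For HAE events reported with missing start date and/or time, stop date and/or time", or with a missing worst-over date or time. When the stop date and time are both missing, the rule is: "The stop date will be set to the worst over date, or if missing, the event start date", with the stop time at 11:59PM. A missing worst-over date leads to the same end point: "The worst over date will be set to the start date, the worst over time will be set to 11:59PM". For a missing start time, "The start time will be set to 12:00PM".

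SAP 6.7.5.1 replaces expert confirmation in Part 3 with programmed rules: "Subject-reported attacks must meet the following criteria (applied in order) for inclusion in the adjusted subject-reported rate computation". There are four:

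1. At least one swelling symptom.
2. No alternative explanation given by the subject.
3. Uniqueness: the attack starts more than 24 hours after the previous one ended, "otherwise the event will be combined with and treated as a continuation of the preceding attack".
4. "If untreated, attack must have a duration > 24 hours".

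SAP 6.7.5.5 measures a combined attack from the start of its first record to the end of its last. SAP 6.7.5.1 also keeps an unadjusted subject-reported rate for Part 3, over the entire dosing period only. The SAP does not say how an imputed stop is to be treated in the fourth rule.

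**The concern.** Each rule is reasonable alone. Together, they let a missing date decide whether an attack counts. The imputation gives the attack close to its shortest possible length, and a minimum-length test is then applied to that imputed length. Protocol 5.1 describes symptoms as typically subsiding over 3 to 5 days (72 to 120 hours), so ending on the start date is an unlikely default.

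At stake is the Part 3 effectiveness description. Attack rate, its trend over time and days with symptoms are Part 3 secondary endpoints (Protocol 7.1.9, SAP 3.2.9). Adjusted attacks feed the monthly Part 3 rate (Table 14.2.2.1.P3), the symptom-day summary (Table 14.2.5.1.1.P3) and the attack-free proportion (SAP 8.8.1). Part 3 requires neither investigator follow-up of attacks nor expert confirmation (Protocol 11.4.2.1), so the programmed rules decide inclusion.

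The SAP's other date rules lean the other way. A missing medication end day goes to the end of the month, and adverse events follow the same convention (SAP 6.8.3 and 6.8.4).

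**Working it through.** The documents give no figure on this point to reproduce. The inputs are the imputed stop, worst-over and start times (SAP 6.8.6), the strict threshold of more than 24 h = 1,440 min (SAP 6.7.5.1), the merging rule (SAP 6.7.5.1) and the duration of a merged attack (SAP 6.7.5.5). Times are in minutes after midnight on the start date, so 11:59PM is 23 × 60 + 59 = 1,439.

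**Stand-alone attack, stop date and time missing, worst-over date missing or equal to the start date.** Duration = 1,439 − s, where s is the start minute (0 to 1,439).
- Longest, s = 0: 1,439 min = 23 h 59 min.
- Start time also missing, s = 720: 719 min = 11 h 59 min.
- Start minutes giving more than 1,440 min: 0 of 1,440.

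**The same, but with a worst-over date one day later.** Duration = 1,439 + 1,440 − s, from 1,440 to 2,879 min. It exceeds 1,440 for 1,439 of 1,440 start minutes (all but 11:59PM). The automatic failure is thus confined to the same-day fallback.

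**Merging, which is applied before duration.**
- The earlier attack runs from Day 1 10:00 to Day 2 20:00, and a record with no stop starts on Day 3 at 10:00. The gap is 14 h, so they merge. Day 1 10:00 to Day 3 23:59 is 61 h 59 min, which passes.
- A no-stop record starts on Day 1 at 08:00 (imputed end 23:59) and another on Day 2 at 20:00. The gap is 20 h 1 min, so they merge. Day 1 08:00 to Day 2 23:59 is 39 h 59 min, which passes.

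**Size.** Let u be the untreated share of attacks that should qualify, and m the share of those lost through this route. The adjusted rate then falls by the fraction u × m. Neither is given. If m is assumed to be 2% to 10%, the untreated component falls by 2% to 10% and the whole rate by u times that. This range is purely illustrative.

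**The case against.** The strongest reply is that the case is narrow, the attack remains visible elsewhere, and little rests on Part 3 effectiveness. Several inferences that a reader might draw do go too far.

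- *Every untreated attack with missing dates is lost.* Not so. Merging comes before duration. After an imputed end at 11:59PM on Day 1, any Day 2 record that reaches the uniqueness step is at most 24 h away and is combined. Symptoms on following days may therefore rescue the attack if they are stored as separate records. The documents do not show whether they are.
- *The attack is deleted.* It leaves the adjusted rate and what is built on it. It remains in the unadjusted Part 3 rate (Table 14.2.1.18.P3) and the subject-reported listings (16.2.6.1.3.ES and 16.2.6.1.5.ES).
- *A missing stop time is enough.* With a stop date present, the attack ends at 11:59PM on that date.
- *The imputation rule can only lower the rate.* An early imputed stop can also split a treated attack. If it is imputed to end on Day 1 at 23:59 and a second treated record starts on Day 3, the gap is at least 24 h 1 min and two attacks are counted. The downward direction holds for the duration exclusion, not for the rule as a whole.
- *Diary completion will decline in Part 3.* The documents do not support this. They provide for diary review at visits, contact for noncompliance, calls about recording and retraining below 90% compliance (Protocol 10.3.5.1, 11.4, 11.4.2.2).

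It is also fair that Part 3 is open-label with safety endpoints as primary, and that hypothesis testing is confined to Part 1 (SAP 8.3).

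These points limit the concern but do not remove it. The unadjusted rate applies none of the four rules and is not produced by month, so comparing it with the adjusted rate cannot isolate attacks lost to imputed times. Site staff may not enter or change diary data (Protocol 11.4).

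**Conclusion.** The point holds for a defined case: a Part 3 attack that is untreated, is not merged with a neighbour, has stop date and time missing, and has a worst-over date that is missing or equal to the start date. Its imputed duration cannot exceed 23 h 59 min, so it is always excluded from the adjusted rate, however long it really lasted. That lowers the adjusted Part 3 rate and the symptom-day count and can raise the attack-free proportion.

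The frequency is unknown and no numerical bias can be claimed. The conclusion assumes that SAP 6.8.6 is applied before the Part 3 criteria, which its general scope implies and nothing in the SAP contradicts. The more-than-24-hours test plays no part in the Part 1 primary analysis, which uses expert-confirmed events. This is a minor but worthwhile clarification.

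**What to change.** In SAP 6.8.6, when the stop date is missing, set it to the last consecutive diary day with symptoms reported for that attack, and use the existing fallback only when no such diary data exist. The diary already asks every day about symptoms in the previous 24 hours (Protocol 11.4), so no new data are needed.

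List every Part 3 attack whose inclusion depends on an imputed stop. Add one sensitivity analysis of the adjusted Part 3 rate that keeps attacks excluded solely on an imputed duration. Treating the duration test as met whenever dates are missing would lean the other way, so it belongs in that sensitivity analysis and not in the main rule.

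The cost is one SAP sentence, minor programming, one listing and one extra summary. The adjusted Part 3 rate may come out slightly higher.

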7. STUDY POPULATION

7.1. Subject Disposition

A summary table will be generated to provide the number and percentage (based on subjects randomized) of subjects in each of the analysis populations.

Subject status at the end of Part 1 will be listed and summarized as a Part 1 only display based on the ITT population, showing the number and percentage of subjects with early discontinuation of study treatment and early withdrawal from the study along with reasons for each item. Subjects will be considered to have completed Part 1 if they have a Week 24 visit. A similar summary table and listing will be provided at the end the study and will show discontinuations over the entire study period. The listings will include whether subjects discontinued from the study drug, whether they withdrew from the study and the reasons for the discontinuation of study drug, along with the date of first and last dose and the date of completion or discontinuation from the study drug and date of study withdrawal. Duration on study treatment and on the study will also be provided.

A CONSORT diagram will be created based on the summary tables for the study report, starting with the number of subjects screened.

A summary of enrollment by investigator site will be provided.

7.2. Screen Failures

The number of screen failures and percent of screened subjects who are screen failures will be summarized along with reasons for screen failure. A summary and listing of demographic information for screen failures will be provided.

Confirmation of clinical diagnosis of HAE will be summarized based on the protocol inclusion criterion: C1 esterase inhibitor (C1-INH) functional levels, complement 4 (C4) levels, SERPING-1 gene mutation, and family history.

Additionally, SERPING result listings will show whether tested subjects were positive or negative for the SERPING-1 gene mutation and hence whether they failed screening due to a negative SERPING result.

7.3. Protocol Deviations and Listing of Subject Inclusion and Exclusion Criteria

Subjects who were randomized but did not satisfy all inclusion and exclusion criteria will be listed. A listing of subjects for whom the treatment blind was broken during the study will also be provided, if appropriate.

Protocol deviations will be included in listings and summaries for the CSR. A separate document will detail decision-making guidelines for determining whether a protocol deviation is major or minor and, for major protocol deviations, whether they would result in exclusion from the PP population. It will also detail a list of categories of protocol deviations. Protocol deviations will be reviewed in data review meetings prior to Part 1 unblinding to classify protocol deviations into categories, determine whether they are major or minor and to determine whether they will result in exclusion from the PP population.

Analyses based on the PP population will only be produced for Part 1 analysis.

A summary of all protocol deviations by type of deviation will be provided for Part 1.

A review of protocol deviations for Part 2 will be conducted prior to database lock for the final study report after the last subject has completed Part 2. Protocol deviations for Part 2 will be summarized by Part 2 treatment (Table 7) and category of deviation and will be listed but will not result in exclusion from the PP population.

7.4. Demographic and Baseline Characteristics

Demographic summary tables will be provided separately for Part 1 Treatment and Part 2 Treatment (Table 7). The ITT and PP populations will be the primary populations for analyses of demographics. Demographics, including age, gender, race, ethnicity, childbearing potential, weight, height, and body mass index (BMI) will be listed and summarized. Age (in years) will be reported as the age at consent or assent, as collected in the eCRF.

BMI (kg/m²) will be calculated using the standard formula:

$$\text{BMI (kg/m}^2\text{)} = \text{Weight (kg)} / [\text{Height (m)}]^2$$

Confirmation of clinical diagnosis of HAE will be summarized based on the protocol inclusion criterion: C1-INH functional levels, C4 levels, SERPING-1 gene mutation, and family history. All SERPING results will be listed.

Baseline C1-INH antigenic levels will be summarized using descriptive statistics for the continuous measure and categorized into < lower limit of normal (LLN) and ≥ LLN; subjects who take Cinryze or Berinert within 72 hours or Ruconest within 24 hours will be excluded from

the categorization but included in the continuous summary. A scatter plot of baseline C1-INH antigenic levels vs. screening C1-INH functional levels will be produced.

7.5. HAE Medical and Medication History

HAE and HAE medication history will be summarized for the following where possible:

- HAE history
- Past on-demand treatments of HAE
- Current on-demand treatments of HAE
- Past prophylactic treatments of HAE

Past on-demand treatments will include those medications that were taken as needed and discontinued prior to the initiation of study treatment as recorded on the HAE Medication History Page. Past prophylactic treatments will include those medications that were taken as prophylaxis and discontinued prior to the initiation of study treatment as recorded on the HAE Medication History Page. Current on-demand medications will include those that are noted at screening as currently used for on-demand treatment as recorded on the HAE Medication History Page. Summaries will include a grouping of any C1-INH medication as well as displays of individual medications. The C1-INH grouping will include plasma-derived C1-INH replacement (brand names = Cinryze, Berinert, HAEgarda), recombinant C1-INH replacement (brand name = Ruconest), icatibant (Brand name = Firazyr), and fresh frozen plasma. The summary of androgens will include androgens (unspecified), oxandrolone, danazol (brand name = Danocrine), and stanozolol.

All HAE medical and medication history collected on the CRF will be listed. Summaries will include a grouping of any C1-INH medication as well as displays of individual medications.

7.6. Medical History and Medical Conditions Present at Entry

Past or current relevant medical history information will be summarized and listed.

7.7. Prior and Concomitant Non-HAE and HAE Medications

Medication use is collected for the period from 30 days prior to Screening to study completion, except for contraceptives which are collected from 60 days prior. Medications collected in the eCRF that were received and stopped prior to the date of first dose will be considered prior medications. Medications will be considered as concomitant if the start date of the medication is on or after the date of first intake of study drug or if the start date is prior to the first date of study drug but the medication is ongoing during the treatment period in the study. Medications taken at any time during Part 1 of the study will be considered with Part 1 treatment. Similarly, medications taken at any time during Part 2 of the study will be considered with Part 2 treatment. For example, a medication which is started during Part 1 while a subject is assigned to a Part 1 treatment of placebo will appear in the Part 1 only summary under the placebo column. If that treatment is continued into Part 2 where the subjects is assigned to a treatment of 110 mg, the medication will also be summarized in the treatment column labeled “110 mg after placebo” in the summary of concomitant medications for the entire study period.

Medication verbatim text will be coded using the WHODD, March 2017. A summary by Part 1 treatment of recently discontinued medications taken within 30 days of screening but discontinued prior to dosing will be provided.

Separate summaries of concomitant medications for Part 1 only and for the entire study period will be presented using the treatment descriptors in [Table 6](#) and [Table 8](#), respectively. The number and percentages of subjects taking each medication will be summarized by WHO preferred name. Multiple uses of the same medication (by preferred name) will be counted once only per subject per study treatment. No inferential statistics will be provided.

HAE-related medications will be similarly summarized for Part 1 only and for the entire study period.

An event-level summary will also be provided showing the number of expert-confirmed events for which the various HAE-related medications were taken based on the subject diary.

All medication data will be listed.

7.8. Baseline Physical Examination

Physical examination data will be listed.

7.9. Baseline Primary and Secondary Efficacy Evaluations

All events will be listed. The baseline event rate and the categorized baseline event rate will be summarized by Part 1 treatment using descriptive statistics for baseline event rate and n [%] for the categorized baseline event rate. The proportion of days with HAE symptoms during the baseline period will also be included in the summary.

Similarly, a summary of baseline of AE-QoL total and domain scores will be provided by Part 1 treatment.

8. EFFICACY

8.1. General Considerations

Data from all centers will be combined for analysis.

Hypothesis tests will be 2-sided. Hypotheses comparing each of the 2 active dose groups to placebo will be separately tested for the primary efficacy endpoint for Part 1 of the current study and the combined Studies 301 and 302 using the ITT populations. Analyses of Part 2 data will be descriptive and will be reported for the current study only. No hypotheses will be tested for Part 2 nor will hypothesis testing be conducted to compare the 2 active dose groups.

8.2. Testing Statistical Assumptions Including Comparability at Baseline

A summary of subgroup membership for the current study and for the combined Studies 301 and 302 will be provided by Part 1 treatment. Subgroups are listed in [Section 8.4](#). In addition, the duration of baseline period, baseline event rate, categorized baseline event rate (≥ 2 events/month vs. < 2 events/month), and baseline AE-QoL will be summarized by Part 1 treatment.

8.3. Statement of the Null and Alternate Hypotheses

Hypothesis testing will be conducted for Part 1 only. The primary null and alternative hypotheses, for each active dose separately, are:

- $H_0: R_A = R_P$; active treatment does not have a differential effect on the rate of expert-confirmed HAE events
- $H_A: R_A \neq R_P$; active treatment does have a differential effect on the rate of expert-confirmed HAE events

where R_A is the monthly event rate for active treatment and R_P is the monthly event rate for placebo treatment.

Secondary hypotheses are (in order of hierarchical testing):

1. Proportion of days with angioedema symptoms

- $H_0: \beta = 0$; active treatment does not have a differential effect on the proportion of days with angioedema symptoms over the entire treatment period
- $H_A: \beta \neq 0$; active treatment does have a differential effect on the proportion of days with angioedema symptoms over the entire treatment period

where β is the parameter representing treatment effect for the dose of interest in an analysis of covariance (ANCOVA) model.

2. Rate of expert-confirmed HAE events during the effective dosing period (beginning on Day 8 through 24 weeks)

- $H_0: R_A = R_P$; active treatment does not have a differential effect on the rate of expert-confirmed HAE events during the effective dosing period
- $H_A: R_A \neq R_P$; active treatment does have a differential effect on the rate of expert-confirmed HAE events during the effective dosing period

where R_A is the monthly event rate for active treatment and R_P is the monthly event rate for placebo treatment during the effective dosing period.

3. AE-QoL

- $H_0: \beta = 0$; active treatment does not have a differential effect on the change from baseline AE-QoL at Week 24
- $H_A: \beta \neq 0$; active treatment does have a differential effect on the change from baseline AE-QoL at Week 24

where β is the parameter representing treatment effect for the dose of interest in a mixed-effects model with repeated measures (MMRM).

